## 2. SYNOPSIS

Title of Study:	Safety and Performance of MINITAC ◇ Ti 2.0 Suture Anchor in Extremities
Study Design:	A retrospective, multi-center, case series
Study Type:	Post-market, clinical follow-up study, non-interventional
Study Product:	MINITAC ◇ Ti 2.0 Suture Anchor
Study Purpose:	Post-market clinical follow-up to support Notified Body (BSI) requirements for extremities repair indications.
Primary Objective:	Assess safety and performance of the MINITAC ◇ Ti 2.0 Suture Anchor in extremities over a time period of 6 months after intervention.
Secondary Objective:	Assess safety and performance of the MINITAC ◇ Ti 2.0 Suture Anchor in extremities over a time period of 12 months after intervention.
Sample Size:	
The study sample was decided based on the feasibility of recruitment, enrollment and follow-up considerations. A minimum of 30 subjects (minimum of 10 subjects per site) up to a maximum of 50 subjects will be enrolled.
 
It is reasonable to estimate a clinical success rate of 95% for the MINITAC◇ Ti 2.0 Suture Anchor in this study. As a result, the probability of estimating the 95% Confidence Interval for the clinical success of 95% to be between 85% and 100% is between 55.4% and 98.8% for 30 to 50 subjects.

Number of Study Sites:	Up to 3 sites
Targeted Global Regions:	Australia and EU (European Union)

Study Protocol—Device	
Safety and Performance of MINITAC◇ Ti 2.0 Suture Anchor in Extremities	Number: MINI.PMCF.2018.11
	Version: 3.0, 20Aug19
	Page: Page 5 of 56

Inclusion Criteria:	
 
1. Subject has undergone extremities repair using the MINITAC◇ Ti 2.0 Suture Anchor.
 
2. Subject was <math>\geq</math> 18 years of age at time of surgery.
 
3. Subject status is <math>></math> 12 months post-operative.
 

Exclusion Criteria:	
 
1. Subject is entered in another investigational drug, biologic, or device study or has been treated with an investigational product within 12 months post-operative.
 

Study Duration:	The expected timeline for the study is approximately two years from first site initiation until final study report.
Primary endpoint:	Clinical success rate (%) of the MINITAC ◇ Ti 2.0 Suture Anchor in extremities at 6 months post-operative with clinical success defined as extremity repairs without signs of device failure and/or re-intervention as assessed by the surgeon.
Secondary endpoint(s):	Clinical success rate (%) of the MINITAC ◇ Ti 2.0 Suture Anchor in extremities at 12 months post-operative with clinical success defined as extremity repairs without signs of device failure and/or re-intervention as assessed by the surgeon.
Other exploratory endpoint(s):	
Surgeon Reported Outcomes based on data collected in the subject's medical chart as standard of care at study sites. This may include but is not limited to the following:
 
 
• Range of Motion (ROM)
 
• Pain assessed by Visual Analogue Scale (VAS)
 
• Listing of device failure criteria.
 

Safety Data	
 
• All adverse events (AEs) and complications occurring from the time of subject enrollment until study termination or study completion including intra-operative adverse events and complications.
 

Study Protocol—Device	
Safety and Performance of MINITAC◇ Ti 2.0 Suture Anchor in Extremities	Number: MINI.PMCF.2018.11
	Version: 3.0, 20Aug19
	Page: Page 6 of 56

	
 
• Device related re-interventions.
 
• Device Deficiencies.
 

--	--

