#### **8.3.3 Subject Attrition**

Subject attrition due to reduction in sample size required for precision analysis has been accounted in the sample size calculation so that the estimate of the Confidence Interval (CI) to be obtained will still be valid through the most efficient use of available subjects.

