## 10.1 GENERAL

Smith & Nephew's Global Biostatistics group or designee will conduct the statistical analysis for this study. Unless otherwise stated, all significance tests will be two-sided, performed at the 5% significance level. Resulting p-values will be quoted. Point estimates and their corresponding 95% two-sided confidence intervals will be generated where appropriate. Where data summaries are specified, categorical and ordinal variables will be summarized with frequencies and percentages. Continuous variables will be summarized with the following summary statistics: number of observations, mean, median, standard deviation, minimum and maximum values. All analyses will be performed in SAS 9.3 (or later).

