## 10.4 EFFICACY ANALYSIS

### 10.4.1 Analysis of Primary Endpoint

Clinical success rate at 6 months will be summarized using frequency (N) and percentage (%). A 95% exact CI for a single proportion will be presented for clinical success at 6 months using the Clopper-Pearson method (1934) (4). This analysis will be carried out using the PP population as the primary analysis population with the SAF population used for sensitivity analysis.

Study Protocol—Device	
Safety and Performance of MINITAC® Ti 2.0 Suture Anchor in Extremities	Number: MINI.PMCF.2018.11
	Version: 3.0, 20Aug19
	Page: Page 29 of 56

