## 11. SAMPLE SIZE JUSTIFICATION

This study is precision-based, as a result, the sample size is not based on statistical power calculations.

It is reasonable to assume a success rate of 95% for the MINITAC◇ Ti 2.0 Suture Anchor in this study. With a further assumption of a  $\pm 10\%$  precision in order to obtain a 95% CI of 85% to 100%, enrolling 30 subjects into the study will provide 55.4% probability. Across all investigational sites therefore, a minimum of 30 subjects (minimum of 10 subjects per site) up to a maximum of 50 subjects overall (98.8% probability) across all sites will be enrolled into this study.

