5.7 Determination of Sample Size

This study is precision-based, as a result, the sample size is not based on statistical power calculations. It is reasonable to assume a success rate of 95% for the MINITAC[◇] Ti 2.0 Suture Anchor in this study. With a further assumption of a $\pm 10\%$ precision in order to obtain a 95% CI of 85% to 100%, enrolling 30 subjects into the study will provide 55.4% probability. Across all investigational sites therefore, a minimum of 30 subjects (minimum of 10 subjects per site) up to a maximum of 50 subjects overall (98.8% probability) across all sites will be enrolled into this study.

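### The stated 55.4% to 98.8% is the chance that the CI half-width is at most 10 points; the chance that the CI lies within 85–100% is 21.5% (n=30) and 54.1% (n=50)

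*Protocol*

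**What the plan says.** The synopsis sets enrolment as follows: "A minimum of 30 subjects (minimum of 10 subjects per site) up to a maximum of 50 subjects will be enrolled". It assumes a true success rate of 95% and then states that "the probability of estimating the 95% Confidence Interval for the clinical success of 95% to be between 85% and 100% is between 55.4% and 98.8" per cent for 30 to 50 subjects.

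Protocol section 11 calls the study precision-based, adds a precision of ±10%, and says that "in order to obtain a 95% CI of 85% to 100%, enrolling 30 subjects into the study will provide 55.4% probability", with 98.8% for 50 subjects. SAP 5.7 carries the same text ("enrolling 30 subjects into the study will provide 55.4% probability").

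The interval is specified in protocol 10.4.1: "A 95% exact CI for a single proportion will be presented for clinical success at 6 months using the Clopper-Pearson method". Protocol 10.1 makes it two-sided at 95%. Protocol 8.3.4 refers to a range, fixed in advance, that the CI for the primary outcome is expected to fall inside.

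On losses, protocol 8.3.3 says: "Subject attrition due to reduction in sample size required for precision analysis has been accounted in the sample size calculation". No attrition rate is given in either document.

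**The concern.** The event described is that the realised CI sits inside a fixed range, with its lower limit at or above 85%. A precision of ±10 points is a different event: it limits the width of the interval and says nothing about where it lies. The two would agree only if the estimate were exactly 95% and the interval symmetric around it (cut off at 100%). Neither can be relied on, because the estimate varies and the exact interval is strongly asymmetric near 100%.

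This probability is the only numerical support for the sample size, in a study run to meet a Notified Body's post-market requirements. A reader would conclude that 50 subjects make a CI above 85% almost certain. If the figures answer another question, that reassurance is false. The attrition sentence adds a second assurance that the calculation may not support.

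**Working it through.** **Inputs.** True success rate p = 0.95 (synopsis; protocol 11; SAP 5.7). n = 30 and n = 50 (same places). Two-sided 95% Clopper-Pearson interval (protocol 10.1 and 10.4.1). Target range 85–100% and precision ±10 points (protocol 11; SAP 5.7).

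**Method.** Let X be the number of successes, X ~ Bin(n, 0.95). For each x, take the interval from L(x) to U(x), where L is the 2.5% quantile of Beta(x, n−x+1) and U the 97.5% quantile of Beta(x+1, n−x), with U = 1 when x = n. Then add P(X = x) over the results that satisfy the criterion:

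- half-width: (U − L)/2 ≤ 0.10
- containment: L ≥ 0.85 (U cannot exceed 1)

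| Result | 95% CI | Half-width (points) | Half-width ≤ 10? | Within 85–100%? | P(X ≥ x) |
|---|---|---|---|---|---|
| 30/30 | 88.4–100% | 5.79 | yes | yes | 0.2146 |
| 29/30 | 82.8–99.9% | 8.57 | yes | no | 0.5535 |
| 28/30 | 77.9–99.2% | 10.63 | no | no | 0.8122 |
| 48/50 | 86.3–99.5% | 6.61 | yes | yes | 0.5405 |
| 47/50 | 83.5–98.7% | 7.65 | yes | no | 0.7604 |
| 44/50 | 75.7–95.5% | 9.89 | yes | no | 0.9882 |
| 43/50 | 73.3–94.2% | 10.46 | no | no | 0.9968 |

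**Reproducing the stated figures (half-width criterion).**

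- n = 30 needs X ≥ 29: 0.95^30 + 30 × 0.05 × 0.95^29 = 0.2146 + 0.3389 = 0.5535, the stated 55.4%.
- n = 50 needs X ≥ 44: P = 0.9882, the stated 98.8%.

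**The event the text describes (containment).**

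- n = 30 needs 30/30: 0.95^30 = 0.2146, or 21.5%.
- n = 50 needs X ≥ 48: 0.0769 + 0.2025 + 0.2611 = 0.5405, or 54.1%.

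The gap is the probability of results that are narrow enough but reach below 85%: 0.3389 at n = 30 (one failure), and 0.2199 + 0.1360 + 0.0658 + 0.0260 = 0.4477 at n = 50 (three to six failures).

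**Whether another reading rescues the figures.** Taking the lower limit ≥ 85% criterion with other intervals:

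| Interval | n = 30 | n = 50 |
|---|---|---|
| Wald | 55.4% | 76.0% |
| Jeffreys | 55.4% | 54.1% |
| Wilson | 21.5% | 54.1% |
| Agresti-Coull | 21.5% | 54.1% |
| 90% Clopper-Pearson | 55.4% | 76.0% |

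None gives 98.8% at n = 50. Under the half-width criterion, Agresti-Coull matches at n = 30 but gives 99.7% at n = 50. Of the readings tried, only the 95% Clopper-Pearson half-width reproduces both numbers.

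**Between 30 and 50.** Neither probability rises steadily with n. Containment ranges from 17.5% (n = 34) to 59.4% (n = 46). The half-width probability falls to 52.0% at n = 32, so even with the right label, 55.4% is not the minimum over the range.

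**Attrition.** Both stated figures come out at exactly n = 30 and n = 50, with no loss. The documents give no rate, so the rates below are assumptions; the last column is P(half-width ≤ 10 points).

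| Enrolled | Assumed loss | Evaluable | Probability |
|---|---|---|---|
| 30 | 10% | 27 | 60.6% |
| 30 | 20% | 24 | 29.2% |
| 50 | 10% | 45 | 92.7% |
| 50 | 20% | 40 | 86.2% |

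The rise to 60.6% reflects the saw-tooth behaviour of exact intervals: at 27 evaluable, one failure still gives a half-width below 10 points (9.44), while at 24 it does not (10.51).

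**The case against.** The best defence is that this is a labelling slip rather than a design error. Protocol 11 and SAP 5.7 do name ±10% precision, and for that criterion both probabilities are correct. The synopsis says the sample was set on feasibility, so the probability describes the size more than it determined it. Nothing in the plan makes 85% a performance goal, and no hypothesis is tested. That much is true, and it is why no change in enrolment follows. It does not make the text right: sections 11 and 5.7 still equate the precision with a CI of 85–100%, and the synopsis does not mention half-width at all.

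A second objection is that SAP 5.2 and 5.8 drop confidence intervals altogether, so neither probability describes a planned output. That is a separate inconsistency. SAP 5.7 still repeats the figures as current text, and SAP 5.8 does not list them as changed.

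On attrition, one could argue that the 30-to-50 range itself absorbs losses: 50 enrolled with 40% lost leaves 30. The documents do not say so, and the 98.8% belongs to 50 evaluable subjects, so the claim in 8.3.3 remains unsupported. How much a loss would matter depends on a rate the plan does not give.

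**Conclusion.** The concern holds. As worded, the probability is overstated by 33.9 percentage points at n = 30 (55.4% against 21.5%) and by 44.8 points at n = 50 (98.8% against 54.1%, from the unrounded values). At the minimum enrolment a single failure puts the lower limit below 85%; at the maximum the chance of meeting the target is a little better than even. The result rests on the plan's own inputs: a true rate of 95%, a two-sided 95% Clopper-Pearson interval, and 30 or 50 evaluable subjects. The attrition statement is not borne out by the calculation, because both figures use the full enrolment; the size of that effect cannot be fixed without an assumed loss rate.

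**What to change.** Correct the synopsis, protocol section 11 and SAP 5.7 in one of two ways:

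- Keep the numbers and change the event: the probability that the half-width of the exact 95% CI is at most 10 percentage points is 55.4% at n = 30 and 98.8% at n = 50. Remove the link to 85–100%, and give these as values at the two sample sizes rather than as a range.
- Keep the 85–100% target and change the numbers: 21.5% at n = 30 and 54.1% at n = 50.

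Bring the reference in protocol 8.3.4 to a pre-defined range for the CI into line with the choice. In protocol 8.3.3, delete the statement that attrition is accounted for, or state an expected loss and give the probabilities for the resulting number of evaluable subjects. When SAP 5.7 is edited, reconcile it with SAP 5.2 and 5.8, which currently remove the interval whose precision it describes.

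The cost is a wording change in the protocol and SAP, and, if the 85–100% target is kept, a less favourable figure. No subjects are added, and neither the endpoint nor the enrolment limits change.

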## **7. SUBJECT ENROLLMENT AND WITHDRAWAL**

### **7.1 SUBJECT POPULATION**

A minimum of 30 and a maximum of 50 subjects should be enrolled into the study at up to 3 sites.

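### The Synopsis gives 55.4% to 98.8% as the precision probability for 30 to 50 subjects, but by the rule that yields both figures it falls to 52.0% at 32 subjects

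*Protocol*

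**What the plan says.** The Synopsis (Sample Size row) allows 30 to 50 subjects, takes 95% as the expected success rate, and describes the probability that the 95% confidence interval lies between 85% and 100%. It says that this probability "is between 55.4% and 98.8% for 30 to 50 subjects".

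Protocol section 11 gives the same figures more carefully. It states a precision of plus or minus 10% ("precision in order to obtain a 95% CI of 85% to 100" percent) and says that "enrolling 30 subjects into the study will provide 55.4% probability". It gives 98.8% for the maximum of 50. SAP section 5.7 repeats this: "up to a maximum of 50 subjects overall (98.8% probability) across all sites will be enrolled into this study".

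The final number is not fixed in advance. Protocol section 7.1 says: "A minimum of 30 and a maximum of 50 subjects should be enrolled into the study".

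**The concern.** The Synopsis sentence, read as written, bounds the probability over every enrolment from 30 to 50. It takes the two end values as the lowest and highest. For an exact binomial interval the probability is saw-toothed in the sample size. While the number of tolerable failures stays the same, each added subject makes it harder to stay within that number, and the probability falls. When one more failure becomes tolerable, it jumps.

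The study describes itself as precision-based and makes no power calculation, so this probability is its only quantitative support for the sample size. If the lower limit is wrong, a study ending at 31 or 32 subjects has a smaller chance of the target precision than the Synopsis states, and a smaller chance than one ending at 30.

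**Working it through.** **Inputs from the documents**
- True success rate 0.95 (Protocol section 11: "It is reasonable to assume a success rate of 95% for the MINITAC").
- Exact interval (Protocol section 10.4.1: "A 95% exact CI for a single proportion will be presented for clinical success at 6 months using the Clopper-Pearson method").
- Two-sided, 2.5% in each tail (Protocol section 10.1: "Point estimates and their corresponding 95% two-sided confidence intervals will be generated where appropriate").
- Precision of plus or minus 10 percentage points (Protocol section 11).
- N from 30 to 50 (Protocol section 7.1).

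**Rule.** Let F be the number of failures, F ~ Binomial(N, 0.05). For each F, compute the Clopper-Pearson limits and the half-width (upper − lower)/2. Let k be the largest number of failures with half-width ≤ 0.10. The precision probability is P(F ≤ k).

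**Step 1: reproduce the plan's figures**
- N = 30. One failure gives the interval 0.8278 to 0.9992, half-width 0.0857. Two failures give 0.7793 to 0.9918, half-width 0.1063. So k = 1, and P = 0.2146 + 0.3389 = 0.5535, the stated 55.4%.
- N = 50. Six failures give 0.7569 to 0.9547, half-width 0.0989. Seven give 0.7326 to 0.9418, half-width 0.1046. So k = 6, and P = 0.9882, the stated 98.8%.

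Half-width rules based on the Wald, Wilson, Jeffreys or Agresti-Coull interval, and the rule that the lower limit is at least 85% under each method, do not give both figures.

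**Step 2: apply the same rule between the ends**
- N = 31. Two failures give half-width 0.1032, so k is still 1. P = 0.2039 + 0.3327 = 0.5366.
- N = 32. Two failures give half-width 0.1002, so k is still 1. P = 0.1937 + 0.3263 = 0.5200.
- N = 33. Two failures give half-width 0.0974, so k = 2. P = 0.7728.

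| N | k | Probability |
|---|---|---|
| 30 | 1 | 55.4% |
| 31 | 1 | 53.7% |
| 32 | 1 | 52.0% |
| 33 to 37 | 2 | 77.3% falling to 71.8% |
| 38 to 41 | 3 | 88.0% falling to 85.3% |
| 42 to 45 | 4 | 94.3% falling to 92.7% |
| 46 to 49 | 5 | 97.4% falling to 96.5% |
| 50 | 6 | 98.8% |

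The minimum is 52.0% at N = 32 and the maximum 98.8% at N = 50. The shortfall against 55.4% is 55.4 − 53.7 = 1.7 points at N = 31 and 55.4 − 52.0 = 3.4 points at N = 32. No other size falls below 55.4%.

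**Step 3: the event as the Synopsis words it.** The Synopsis speaks of the interval lying within 85% to 100%, which means a lower limit of at least 0.85. That is a different event:
- N = 30: no failures allowed (one gives a lower limit of 0.8278). P = 0.95^30 = 21.5%.
- N = 32: no failures allowed. P = 0.95^32 = 19.4%.
- N = 34: no failures allowed (one gives 0.8467). P = 0.95^34 = 17.5%, the minimum over 30 to 50.
- N = 46: two failures allowed (lower limit 0.8516). P = 59.4%, the maximum.
- N = 50: two failures allowed. P = 54.1%.

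Here too the values at 30 and 50 are not the extremes.

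**The case against.** The strongest reply is that the Synopsis merely compresses Protocol section 11, pairing 30 with 55.4% and 50 with 98.8% in order, and that nobody promised a minimum over the sizes between. This stands for section 11 and SAP section 5.7, which attach each figure to its own sample size and are correct there by the half-width rule. It does not rescue the Synopsis, whose wording gives a range for 30 to 50 subjects.

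Second, the effect is small and sits close to the cut-off. At N = 32 the half-width with two failures is 10.02 points against a limit of 10. If that counted as meeting the target, the probability there would be about 78.6% and the minimum would be 53.7% at N = 31, a gap of 1.7 points. This is true, but the stated lower limit would still be too high.

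Third, no decision turns on it. The Synopsis says that the sample was chosen for feasibility, and nothing in the protocol makes stopping depend on this probability. SAP sections 5.2 and 5.8 also drop confidence intervals from the analysis, so the quantity has little practical use while that stands. This limits the weight of the point, not its correctness.

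A reader might infer more: that 55.4% and 98.8% were miscalculated, that all three places are wrong, or that 30 to 50 subjects is unsound. The documents support none of these. Both figures reproduce, two of the three places make no range claim, and a 3.4-point difference gives no reason to change the enrolment limits.

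**Conclusion.** The point holds for the Synopsis sentence only. By the rule that reproduces both of the plan's figures, the range over 30 to 50 subjects is 52.0% to 98.8%, not 55.4% to 98.8%. The lower limit is overstated by at most 3.4 points, at 31 and 32 subjects only.

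This rests on a true success rate of exactly 95%, the two-sided Clopper-Pearson interval, a strict 10-point limit on the half-width, and the number analysed equal to the number enrolled. It is a minor error of statement, worth correcting because the study offers no other quantitative basis for its size.

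Replacing the closing numbers alone would not make the sentence true. It would still name the interval lying within 85% to 100%, whose probability at 32 subjects is 19.4%. The correction has to name the event as well.

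**What to change.** Reword the Synopsis sentence so that event and figures match, for example: *At a true success rate of 95%, the probability that the half-width of the exact 95% CI is at most 10 percentage points is 55.4% at 30 subjects and 98.8% at 50 subjects (minimum 52.0%, at 32 subjects).*

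If the sponsor prefers to keep the event as the interval lying within 85% to 100%, quote that event's own range over 30 to 50 subjects: 17.5% (at 34) to 59.4% (at 46).

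Protocol section 11 and SAP section 5.7 need no change on this point. The cost is wording only: no extra subjects and no change to the enrolment limits. With the half-width event the stated minimum becomes slightly less favourable. With the 85% to 100% event the stated figures become much lower.

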## STUDY SCHEDULE

Schedule of Events	Chart Review 		
	Screening	6 months (182 days) post-op (+30/- 150 days)	12 months (365 days) post-op (+ 30/- 150 days)
Inclusion/Exclusion	X		
Demographics/Medical History	X		
Operative Data Collection	X		
Assessment of clinical success (device related re-intervention and/or repair failure)		X	X
Surgeon Reported Outcomes: Pain assessed by VAS 	X	X	X
Surgeon Reported Outcomes: ROM 	X	X	X
Concomitant Medications or Therapies	X	X	X
All Adverse Events or Complications, Device Deficiency (DD)	X	X	X
AE Assessment	X	X	X
End of Study			X

 Given the retrospective study design, data will be collected to the extent it is available.

 Surgeon Reported Outcomes are collected per standard of care.

Study Protocol—Device	
Safety and Performance of MINITAC◇ Ti 2.0 Suture Anchor in Extremities	Number: MINI.PMCF.2018.11
	Version: 3.0, 20Aug19
	Page: Page 7 of 56

### 3.4 LIST OF ABBREVIATIONS AND DEFINITIONS

Abbreviation	Definition
ADE	Adverse Device Effect(s)
AE	Adverse Event(s)
AFOAS	American Orthopaedic Foot & Ankle Society
ASADE	Anticipated Serious Adverse Device Effect(s)
BSI	British Standards Institute
CRF	Case Report Form(s)
CTA	Clinical Trial Agreement
CV	Curriculum Vitae
DD	Device Deficiency(ies)
EC	Ethics Committee
EU	European Union
GCP	Good Clinical Practice
HREC	Human Research Ethics Committee
ICMJE	International Committee of Medical Journal Editors
ID	Identification (ID) number
IFU	Instructions for Use
NA or N/A	Not Applicable
Non-interventional study	A clinical study in which the investigational medical device of interest is used in accordance with the approved instructions for use. Assigning a subject/patient to a particular therapeutic arm is not decided in advance by a protocol but falls within current practice; use of the device is clearly separated from the decision to include the patient in the study. No additional diagnostic or monitoring procedures are used, and epidemiological methods are used to analyse the collected data.
PI	Principal Investigator
PP	Per-protocol Population
ROM	Range of Motion
S&N	Smith & Nephew Orthopaedics AG

Study Protocol—Device	
Safety and Performance of MINITAC® Ti 2.0 Suture Anchor in Extremities	Number: MINI.PMCF.2018.11
	Version: 3.0, 20Aug19
	Page: Page 11 of 56

Abbreviation	Definition
SADE	Serious Adverse Device Effect(s)
SAE	Serious Adverse Event(s)
SAF	Safety population
SAP	Statistical Analysis Plan
UHMW	Ultra-high-molecular-weight
USADE	Unanticipated Serious Adverse Device Effect(s)
VAS	Visual Analogue Scale

Study Protocol—Device	
Safety and Performance of MINITAC◇ Ti 2.0 Suture Anchor in Extremities	Number: MINI.PMCF.2018.11
	Version: 3.0, 20Aug19
	Page: Page 12 of 56

